STU#:00204116

PROTOCOL TITLE: A Comparison of Analgesic Efficacy of Ultrasound-Guided Genicular Nerve Block versus Saline Injection for Total Knee Replacement: a Prospective, Randomized Controlled Trial

PRINCIPAL INVESTIGATOR:

[name]

Institution: Northwestern University, Feinberg School of Medicine

Department: Anesthesiology

Address: [name]

Email Address: [contact]

[contact]

[contact]

VERSION NUMBER: 1.0

VERSION DATE: 09/12/2017

OBJECTIVES:

Research Questions:

Do ultrasound-guided genicular nerve blocks with 0.5% bupivacaine provide improved knee analgesia for patients recovering from total knee replacement surgery compared to saline injection?

Hypotheses:

We hypothesize that the combination of ultrasound-guided adductor canal block (ACB) and genicular nerve block will achieve lower opioid consumption and therefore lead to decreased systemic side effects and improved overall satisfaction compared to ultrasound-guided saline injection for patients undergoing minimally invasive elective total knee arthroplasty (TKA).

BACKGROUND:

Total knee arthroplasty is associated with intense early postoperative pain. A sizeable proportion (25–40%) of patients experience severe pain postoperatively despite a comprehensive multimodal analgesic regimen.¹ Enhanced recovery protocols that emphasize early mobilization and hospital discharge remain varied among hospitals. Regional anesthetic techniques have evolved to preserve motor function in an effort to promote early ambulation and hospital discharge, while optimizing sensory blockade for adequate analgesia. The (ACB) of the saphenous nerve has demonstrated reduced opioid consumption and preservation of quadriceps muscle strength when compared to placebo and to femoral nerve blockade² however, several studies have shown that despite ACB, many patients may still have at least moderate, movement-related pain. This may be partly because the ACB does not provide analgesia to the posterior aspect of the knee, in which pain is commonly moderate to severe after surgery.

It has been proposed in the literature that complete blockade of the knee joint for adequate analgesia requires blockade of the genicular nerves.³ The genicular nerves provide sensory innervation to the joint capsule and internal and external ligaments of the knee joint. The superior and inferior medial genicular nerves arise in the posterior popliteal fossa and are sensory branches of the tibial nerve. The superior and inferior lateral genicular nerves are sensory branches of the common peroneal nerve and course anteriorly to the lateral knee. The identification of the genicular nerves using ultrasound has been described in the literature.⁴

At our institution, all patients scheduled to undergo total knee replacement receive periarticular injections as part of their pain management, as this practice demonstrates effectively reduced narcotic consumption and improved patient satisfaction compared to IVPCA.⁵

We hypothesize that the combination of ultrasound-guided ACB and genicular nerve block will further decrease opioid consumption and therefore lead to decreased systemic side effects and improved overall satisfaction compared to ultrasound-guided adductor canal block alone in patients undergoing elective minimally invasive TKA surgery.

INCLUSION AND EXCLUSION CRITERIA:

Patient inclusion criteria:

Participants 40 to 85 years old who are presenting for minimally invasive total knee arthroplasty under spinal anesthesia and are candidates for peripheral nerve blocks. Minimally invasive is defined as custom modified instrumentation, a quadriceps sparing arthrotomy that does not extend beyond 1cm proximal to the patella and surgical techniques that focus on soft tissue protection.

Patient exclusion criteria:

Patient refusal

American Society of Anesthesiologists physical status classification of 4 or higher
Pre-existing neuropathy in the femoral or sciatic distribution

Coagulopathy

Infection at the site

Chronic opioid use (greater than 3 months)

Pregnancy

Medical conditions limiting physical therapy participation

Any other contra-indication to regional anesthesia

- *Adults unable to consent* N/A
- *Individuals who are not yet adults (infants, children, teenagers)* N/A
- *Pregnant women* N/A
- *Prisoners* N/A

STUDY-WIDE NUMBER OF PARTICIPANTS: N/A

(If this is a multi-center study for which you are the lead investigator, indicate the total number of participants to be accrued across all sites.)

STUDY-WIDE RECRUITMENT METHODS: N/A

MULTI-SITE RESEARCH: N/A

STUDY TIMELINES:

Subject's participation in the study will last 1 year

Approximately 5 TKA surgeries are performed each week at the Feinberg Pavilion. If we are able to enroll 5 subjects per month it should take about 24 months to complete.

STUDY ENDPOINTS:

Primary Outcome:

-Post-operative opioid consumption during the hospital stay.

Secondary Outcome:

-Pain scores (Visual Analog Scale pain score; 0 = no pain, 10 = excruciating pain) in the knee at rest and during activity recorded every 6 hours up to discharge.

- Overall global pain score (VAS pain scores; 0 = no pain, 10 = excruciating pain) recorded every 6 hours up to discharge.
- Overall pain burden for the first 36 hours.
- Opioid related side effects
- Time to physical therapy milestones (active straight leg raise, time until patient first gets out of bed, ambulation about the hospital room with or without assistance, ambulating 100 feet and ability to climb stairs)
- Length of hospitalization
- Readmission to the hospital or emergency room visit for evaluation during study period.

PROCEDURES INVOLVED:

All ASA 1-3, 40-85 year old patients who are scheduled for total knee reconstruction surgery and are scheduled to receive a nerve block as part of their postoperative analgesic care will be approached to participate in this study. Patients will be introduced to the study in the Lavin Pavilion 12th floor pre-operative clinic by one of the study team members. On the day of surgery in the Feinberg pavilion 5th Floor. The subject will be approached by one of the study team members to answer any questions they have regarding the study. If they had not signed the consent document in the pre-operative clinic they will be asked again if they had reviewed the consent document and whether they would like to participate. Patient participation will last for 12 months.

Sealed opaque envelopes will be pre-randomized into two study medication groups using a computerized random number generator.

The study medication and protocol will consist of Group 1 (Active) – ultrasound-guided adductor canal blockade with 10 ml of 0.25% bupivacaine and ultrasound-guided genicular nerve blocks with 6 ml of 0.5% bupivacaine, and Group 2 (Control) – ultrasound-guided adductor canal block with 10 ml of 0.25% bupivacaine and ultrasound-guided genicular nerve blocks with 6 ml of normal saline. The surgeon will be blinded to the subjects study arm assignment.

An ultrasound-guided ACB will be performed at the level of the mid-thigh of the leg halfway between the superior anterior iliac spine and the patella. The femoral artery, femoral vein, saphenous nerve will be visualized by ultrasonography and the expansion of the adductor canal will be recorded. Sensory assessment of the saphenous distribution will be performed at 30 minutes. The ultrasound-guided genicular nerve block will be performed at the site of the superior lateral, the superior medial, and the inferior medial genicular nerves. The superior lateral genicular nerve is located at the confluence of the lateral femoral shaft and the lateral femoral condyle (in the anteroposterior plane) and at the midpoint of the femur (in the lateral plane). The superior medial genicular nerve site is located at the confluence of the medial femoral

shaft and the medial femoral condyle (in the anteroposterior plane) and at the midpoint of the femur (in the lateral plane). The inferior medial genicular nerve site is located at the confluence of the medial tibial shaft and the tibial flare (in the anteroposterior plane) and the midpoint of the tibia (in the lateral plane). Color Doppler will be used to identify the arterial structures which serve as landmarks for the corresponding nerves. All nerve blocks will be performed by a study team physician.

Postoperative follow-up will be done by study team member blinded to the group allocation. The dosing of oxycodone/hydrocodone-acetaminophen will be as needed with management goal of a Visual Analog Scale (VAS) score of ≤ 4 . Patients with pain not managed by oral agents will receive IV medication. Patients will be visited during their hospital stay every six to eight hours until discharge to record pain scores, opioid consumption, and patient satisfaction. In addition, patients will be given a pain diary to record (VAS) pain scores every six hours until hospital discharge.

A study team member will follow up patients by telephone (if discharged prior to) at 48 hours, 72 hours and at 3 weeks and will ask questions pertaining to the patient's pain, narcotic side effects, and satisfaction with pain control. Patients are scheduled to have a follow-up visit with their orthopedic surgeon at approximately 3 weeks and 1 year following surgery. The range of motion, current pain medication use, pain scores and untoward events will be re-recorded during each surgical follow-up visit. Patient's medical record will be reviewed to verify or obtain correct opioid consumption and physical/occupational therapy participation during hospital stay.

DATA AND SPECIMEN BANKING: N/A

DATA AND SPECIMEN MANAGEMENT:

Study members will have an active Collaborative Institutional Training Initiative (CITI) training certification. Their names and roles will be added to the IRB application.

Each study subject will be assigned a study code number. The code will be used to link study data to patient identification (name) in a separate database that only the investigator has access.

Strict measures will be in place to ensure that no loss of confidentiality occurs. Only study team members will have access to the data. The principal investigator will be responsible for handling and management of the data.

Subject data will be stored on password protected secure computer at Northwestern University 10th floor Arkes (Department of Anesthesiology administrative office). Data access will be password protected and only available to study team members. Access will be controlled by the Principal Investigator. Local data will be stored on Northwestern University, NM servers which are password protected and backed up nightly. Information regarding the perioperative course will be included in the data collection. Data will also be validated by the PI prior to data analysis.

Data will be stored on NM Servers and Department of Anesthesiology computers which are password protected. Paper data will be stored in Arkes Pavilion 10th floor Department of Anesthesiology office research closet which is accessible by key card entry and then key for the closet. Each study subject will be assigned a study code number. The code will be used to link study data to patient identification (name) in a separate database.

The data both electronic and paper will be stored for five (5) years after manuscript preparation. Data both electronic and paper will be destroyed using departmental standards and approved vendors.

PROVISIONS TO MONITOR THE DATA TO ENSURE THE SAFETY OF PARTICIPANTS:

At the start of the study, a Data and Safety Monitoring Board (DSMB) will be appointed and will consist of the PI, a regional anesthesiologist, a statistician ([name]) all with expertise in the area of regional anesthesia complications after blocks for orthopedic surgery. The DSMB members must attest to not having any conflicts of interest with the study. A study team member (TBD) will participate in the DSMB meetings as non-voting member. The DSMB will be charged with oversight of the study's safety and integrity and assessing the risk versus benefits of continuing the study if such questions arise. The DSMB will meet annually in person or by conference call or more often, if necessary, based on the progression of the study. The DSMB will continue to meet until the completion of the study.

The DSMB will review patient recruitment and patient follow-up, compliance with the protocol including protocol violations, timeliness and completeness of data entry, compliance with patient confidentiality and HIPPA regulations, and communications of adverse events to the IRB. The DSMB members should immediately review the data in order to make any requests for additional information or analysis in a time frame that can allow for such requests to be completed before the scheduled DSMB meeting. Members of the DSMB must maintain confidentiality of the study data until otherwise instructed. An interim analysis of the data looking at safety will be conducted by the DSMB when results from the first 50 subjects are available.

WITHDRAWAL OF PARTICIPANTS:

If the subject decides to discontinue their participation in the study, no further exams will be completed. The existent data sheet will be preserved and the removal of a partially completed subject from the data set will be noted in the study manuscript. A research team member will contact the PI by secured-email to inform him about the event that led to early study termination.

RISKS TO PARTICIPANTS:

ACB is a widely practiced technique performed to provide postoperative analgesia for patients undergoing total knee arthroscopy. The major risk of genicular nerve block is infection, which is exceedingly rare given the use of aseptic technique.

Subject's involvement may make them feel emotionally uncomfortable because study team members will ask them questions regarding their pain and satisfaction throughout the study period.

The risks of the study medication include unintentional intravascular injection of the local anesthetic solution. This may cause cardiovascular effects such as hypotension, bradycardia, ventricular arrhythmias or cardiac arrest. Allergic response which can be mild or as severe as anaphylaxis. Rare risks include restlessness, anxiety, dizziness or tremors.

There is the risk of loss of confidentiality even though there are strict measures in place to prevent occurrence.

POTENTIAL BENEFITS TO PARTICIPANTS:

The potential benefit of participating in the study is that patients receiving the both the ACB and genicular nerve block may take less pain medication resulting in fewer side effects and achieve physical therapy milestones sooner than those who do not receive an genicular nerve block.

VULNERABLE POPULATIONS: N/A

COMMUNITY-BASED PARTICIPATORY RESEARCH: N/A

SHARING OF RESULTS WITH PARTICIPANTS: N/A

SETTING:

Study participants will be identified and recruited from the Anesthesiology pre-operative clinic on the 17 Floor of Lavin Pavilion at Northwestern Memorial Hospital. The research will be performed in the pre and post-operative area at Feinberg Pavilion 5th Floor. Post-surgery evaluations will occur on the orthopedics floors on the Feinberg Pavilion. The 3 week and 1 year follow up will occur in the orthopedic surgeon's office within Northwestern Medicine.

RESOURCES AVAILABLE:

The Section of Regional Anesthesiology actively provides care to admitted patients at Feinberg Pavilion. As a Regional Anesthesiologist and member of the Anesthesiology Service I regularly supervise and provide care to patients on this unit. We have a dedicated group of study team members that assist with daily recruitment and follow-up of patients in clinical anesthesiology trials. Study team members all have CITI training.

The primary investigator has expertise using the ultra-sonographic probe for needle guidance for nerve blocks. The study team members will set up the ultrasound machine for each study participant.

- The ability to recruit the number of study participants should be fairly easy given the number of TKA performed yearly.
- The investigator will be present for all scheduled study related nerve blocks.
- The study will be conducted in one of pre and post-operative rooms in the PACU on the 5th floor Feinberg Pavilion.
- Participants will have the immediate availability of the supervising anesthesiologist and attending anesthesiologist of record.
- Participating anesthesiologists and operating room staff and study team members will be briefed on the study prior to the subjects block.

PRIOR APPROVALS:

Department of Anesthesiology Research Committee

RECRUITMENT METHODS:

Subjects will be approached and recruited by a member of the anesthesia research team during the pre-operative clinic visit on the 17th floor Lavin Pavilion of Northwestern Memorial Hospital. Study team members will use Powerchart and Epic from NW to screen potential participants

Describe materials that will be used to recruit subjects. N/A

NUMBER OF LOCAL PARTICIPANTS:

On the basis of the literature ⁶ we assumed that patients in Group B (Control group) will have an average opioid consumption at 36 hours following surgery of 48 mg IV morphine equivalents (morEq) while patients who receive genicular nerve blocks would experience a decrease of 20% in opioid consumption to an average of 39 mg IV morEq. Standard deviation was estimated to be 15. The effect size is 0.60. Comparison of means of two independent groups (Wilcoxon-Mann-Whitney Test) demonstrated a required total sample size of 94, 47 participants in each group. 80% power, 0.05 alpha level. Six patients will be added to account for lost to follow up or cancelled surgical cases.

Pain burden defined as the area under the numeric rating score for pain for the first 36 hours will be calculated using the trapezoidal method. Time to report first pain and overall patient satisfaction between groups will be compared using the Kruskal-Wallis H test.

CONFIDENTIALITY:

Data is collected on paper by study team members and then entered onto the Department of Anesthesiology password controlled computers located on the 10th floor Arkes Pavilion. Data are stored in a department (NM) server which is also password protected and backed up nightly. Each study subject will be assigned a study code number. The code will be used to link study data to patient identification (name) in a separate database.

The paper folders will be stored in Arkes Pavilion 10th floor Department of Anesthesiology administrative office via key card controlled front door and key controlled closet. Data access will be password protected and only available to study investigators and study team members. Access to the data is controlled by the principal investigator. Data both electronic and paper will be destroyed 5 years after manuscript preparation using current procedures and approved vendors.

PROVISIONS TO PROTECT THE PRIVACY INTERESTS OF PARTICIPANTS:

The subject will have multiple interactions with the study team. The first interaction will be to discuss and obtain written informed consent; then multiple times during the perioperative period. The brief interactions will limit the amount of intrusion into the subject's recovery process.

The research study team is only to be allowed to view the data sheets, Powerchart and EPIC for selected data within the parameters of the study.

COMPENSATION FOR RESEARCH-RELATED INJURY: N/A

ECONOMIC BURDEN TO PARTICIPANTS:

There is no additional cost to participate. The extra block will be paid for by the Department of Anesthesiology.

CONSENT PROCESS:

The consent process will take place on the 17th Floor Lavin Pavilion, at Northwestern Memorial Hospital. Subjects who have reviewed the document but have not signed prior to the surgical date will be approached again on the day of surgery on the 5th Floor Feinberg Pavilion. The research study team will spent greater than 10 minutes discussing the study. Ample time will be allowed for patient to answer questions regarding the study and the consent document. The subject will also be informed that there is no conflict of interest between the PI and the protocol. The PI will not receive financial remuneration nor will the study participation affect the subject's financial charges for their care.

Waiver or Alteration of Consent Process: N/A

Participants who are not yet adults (infants, children, teenagers):N/A

PROCESS TO DOCUMENT CONSENT IN WRITING:

We will be following HRP-091. Consent attached to EIRB+ application

DRUGS OR DEVICES:

The FDA approved Sonosite M-Turbo Ultrasound Machine will be stored on the 5th floor Feinberg Pavilion at Northwestern Memorial Hospital in the anesthesiology store room behind a locked door. The ultrasound machine is owned by the Department of the hospital and is stickered by biomedical engineering.

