Appendix A

DATA COLLECTION FORM Ultrasound-guided genicular nerve block

Investigator: [name].

Subject: ____ • **Date of procedure:** ____ / ____ / ____ TKA

description: _____

Surgical Procedure: L R

Baseline (24hr) pain score: _____ Sex:

M F Weight: ____ lbs/kg • Height: ____ in Age: ____

Subject Demographics: Caucasian: ____ African American: ____ Asian: ____ Hispanic: ____

Middle Eastern: ____ Other: _____

Time to complete block (needle in–needle out): _____

Time of block placement: ____ Sensory Assessment at 30 minutes: Yes No

Pain Score (VAS 0-10) after the performance of the block: _____

Immediate Complications: None Yes If yes, explain:

Delayed Complications: None Yes If yes, explain:

Follow-up: Time to 1st pain: _____ **Location:** _____

	6hr	12hr	18hr	24hr	30hr	36hr	42hr	48hr
Time:								
NRS (0-10)								
At rest								
During Activity								
Pain medication:								
Norco ____ mg								
Oxycodone								
Dilaudid								
Side effects (0-3)								
1=mild, 2=mod, 3=severe								
Nausea								
Vomit								
Dizzy								
Patient Satisfaction (0-10) Pain Control								

Anterior ____ **Posterior** ____ **Other** _____

Physical Therapy Milestones	Time
Active straight leg raise	
Time until patient first gets out of bed	
Ambulation about the hospital room with or without assistance	
Ambulating 100 feet	
Ability to climb stairs	

Time of Discharge: _____ Date: ____ / ____ / ____ Length of hospitalization: _____

	72hr	3wks
Time:		
NRS (0-10) At rest During Activity		
Pain medication: Norco ____ mg Oxycodone Dilaudid Tramadol		
Side effects (0-3) 1=mild, 2=mod, 3=severe Nausea Vomit Dizzy		
Patient Satisfaction (0-10) Pain Control		

Follow up:

Pain Scores (0-10)

At Rest: @ 3wk _____ and @ 1year _____

During Activity: @ 3wk _____ and @ 1year _____

Block Satisfaction @ 3wk (0-10):

VS S Not Sat nor US US VUS

Range of motion: @ 3wk _____ and @ 1year _____.

Readmission to the hospital or emergency room visit:

Yes No

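### Patients with up to three months of current opioid use can enter a trial whose primary outcome is opioid consumption, and the plan neither records nor uses that baseline variable

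*Protocol*

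**What the plan says.** The exclusion list in the protocol's Inclusion and Exclusion Criteria has one opioid item, "Chronic opioid use (greater than 3 months"). It screens on duration. The inclusion criterion concerns age, type of surgery, anesthesia and suitability for a block, and the recruitment text under Procedures Involved adds no opioid condition.

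Study Endpoints gives the primary outcome as "Post-operative opioid consumption during the hospital stay".

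In Appendix A the baseline entries are "Baseline (24hr) pain score", sex, weight, height, age and race. The medication rows begin at 6 hours after surgery and continue to 48 hours, then 72 hours and 3 weeks. The pain journal (Appendix C) holds pain scores only. Under Procedures Involved, chart review of opioids is confined to the admission: "Patient's medical record will be reviewed to verify or obtain correct opioid consumption and physical/occupational therapy participation during hospital stay". Medication use at the surgeon's visits, about 3 weeks and 1 year after the operation, is post-operative.

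Allocation is to two groups by sealed envelope, with no stratification factor stated. The Wilcoxon-Mann-Whitney test is named only in the sample-size paragraph. The SAP covers pain burden, time to first pain and satisfaction. Neither document mentions pre-operative opioid use in an analysis.

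**The concern.** Recent opioid intake can be expected to bear on how much opioid a patient needs after surgery, which is the quantity this trial measures. The protocol treats prior use as relevant, since it excludes long-term users. For the shorter-term users who remain eligible, it then collects nothing.

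Two things are at stake. The first is precision: if some patients consume more for reasons unrelated to the block, the outcome is more variable, and a sample size set at almost exactly 80% power has little room for that. The second is interpretation: without a baseline record, the report cannot show whether the arms were alike in prior use, cannot adjust the primary comparison, and cannot run a sensitivity analysis on it.

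**Working it through.** **The plan's own figure.** Inputs from Number of Local Participants: control mean 48 mg, active mean 39 mg (both IV morphine equivalents at 36 hours), SD 15, alpha 0.05, power 80%, Wilcoxon-Mann-Whitney test. Sidedness is not stated; two-sided reproduces the result.

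- Effect size: (48 − 39)/15 = 0.60.
- Two-sided t-test: 44.59 per group.
- Divide by the Wilcoxon efficiency 3/π = 0.955: 44.59/0.955 = 46.7, so 47 per group and 94 in total. This matches the plan.
- Power at 47 per group: 80.3%.

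**Adding unmeasured prior use.** Let p be the share of patients with recent use and x their extra consumption in mg. The documents give neither, so both are assumptions. Taking 15 as the SD within users and within non-users:

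SD = √(15² + p(1 − p)x²), and power is then evaluated at d = 9/SD with 47 per arm and the same 3/π correction.

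| p | x (mg) | SD (mg) | d | Power | n per arm for 80% |
|---|---|---|---|---|---|
| 0 | – | 15.0 | 0.600 | 80.3% | 47 |
| 10% | 10 | √(225 + 9) = 15.3 | 0.588 | 78.7% | 49 |
| 10% | 20 | √(225 + 36) = 16.2 | 0.557 | 74.2% | 54 |
| 20% | 20 | √(225 + 64) = 17.0 | 0.529 | 69.9% | 60 |

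A harsher assumption (20%, +30 mg) gives SD 19.2 and power 59.3%. It requires extra intake of 30/48 = 63% of the whole control mean, and the point does not rest on it.

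**Chance imbalance.** At p = 20% and x = 20 mg, with 47 per arm:

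- SD of the between-arm difference in user share: √(2 × 0.2 × 0.8/47) = 0.0825.
- A 2-SD imbalance moves the mean difference by 2 × 0.0825 × 20 = 3.3 mg, which is 3.3/9 = 37% of the target.
- Observed difference needed for significance at SD 17, approximately: 2 × 17 × √(2/47) = 7.0 mg.
- A true 9 mg effect would then be expected to appear as 9 − 3.3 = 5.7 mg, below 7.0 mg, so the effect could be masked.
- To produce 9 mg with no true effect, the user shares would have to differ by 9/20 = 45 percentage points, which is 0.45/0.0825 = 5.5 SD.

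At p = 10% and x = 10 mg the 2-SD shift is 2 × √(2 × 0.1 × 0.9/47) × 10 = 1.2 mg, about 14% of the target.

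**The case against.** The strongest reply is that the size of the problem is assumed throughout. The documents show that such patients may enrol, not how many will. The rows with a material loss need +20 mg, which is 20/48 = 42% of the control mean; the mildest row costs 1.6 percentage points. The SD of 15 comes from literature, and if that population included recent users, part or all of this variance is already in the plan. All of this stands, and it is why the result is given as a range with its assumptions.

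It is also fair to say that chance imbalance is not a second harm on top of the power loss. It is the same variance seen from another side, and the 5% type I error already allows for it. What remains is that a measured covariate would let the analysis remove that variance and let a reader see any imbalance.

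Several stronger readings are tempting, and the documents do not support them:

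- A reader might infer bias. Allocation is random, so prior use is balanced in expectation.
- A reader might infer that imbalance could manufacture the target difference. The 5.5 SD figure rules that out for practical purposes in the scenario worked above.
- A reader might infer that the gap could never be repaired. Staff screen in the electronic record (Recruitment Methods) and Appendix B links each subject to a record number. Later abstraction is unplanned, not impossible.
- A reader might take "The range of motion, current pain medication use, pain scores and untoward events will be re-recorded during each surgical follow-up visit" to promise a pre-operative record that is missing. That list includes untoward events, which have no pre-operative value, and the in-hospital and telephone records explain the verb well enough.
- A reader might object that long-stopped former users could be excluded. Chronic use in an exclusion list ordinarily means a current state, and losing a few former users would not harm the comparison.

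**Conclusion.** The point holds in a limited form. Patients with current opioid use of up to three months are eligible, the primary outcome is opioid consumption, and no form, chart review or analysis captures or uses pre-operative intake. The consequence is lost precision and no planned means of description or adjustment; it does not invalidate the trial.

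Under the stated assumptions, power at 47 per arm runs from about 79% down to about 70%, against the planned 80%. This rests on assumed shares of 10% to 20%, assumed extra intake of 10 to 20 mg, and an SD of 15 that applies within users and within non-users. It also takes the plan's 36-hour figures as representative of the in-hospital outcome. The true loss could be negligible if such patients are few or were already reflected in the source SD. The change is worth making because it costs so little next to the precision and clarity it may protect.

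**What to change.** Add one line to the baseline part of Appendix A: opioid use in the 30 days before surgery (yes/no), with drug, mg per day and duration. Complete it from the chart and the pre-operative clinic visit before the envelope is opened, so that it cannot be influenced by allocation.

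In the SAP, prespecify the primary comparison as stratified by that yes/no variable, for example with a van Elteren stratified Wilcoxon test, which keeps the rank-based approach used for the sample size. A model adjusted for the variable is an alternative. Choose one before any outcome is seen, and tabulate prior use by arm.

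The cost is one form line and a slightly more complex primary analysis. Eligibility need not change; a recency window in the exclusion would still leave a patient with 10 to 12 weeks of daily use eligible. The envelopes need not change either, since two sets without blocking would not ensure balance within strata.

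### The primary outcome is opioid use over the whole hospital stay, but the sample size and 80% power were worked out for opioid use at 36 hours

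*Protocol*

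**What the plan says.** **Endpoint.** Under Study Endpoints in the protocol, the primary outcome is "Post-operative opioid consumption during the hospital stay". No hour is attached. Under Procedures Involved, opioid use is recorded at visits up to discharge, and the medical record is reviewed to "verify or obtain correct opioid consumption and physical/occupational therapy participation during hospital stay". Both fit a total that ends when the patient leaves.

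**Sample size.** Number of Local Participants assumes that control patients "will have an average opioid consumption at 36 hours following surgery of 48 mg IV morphine equivalents (morEq", against 39 mg with the genicular block. It takes an SD of 15 and an effect size of 0.60. A Wilcoxon-Mann-Whitney comparison at 80% power and alpha 0.05 then gives 47 per group, 94 in total, with six more added for losses and cancellations.

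**Where a 36-hour window is written.** One listed outcome carries it, and that outcome is secondary: "Overall pain burden for the first 36 hours". The SAP repeats the window for pain burden and does not mention opioid consumption.

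**Length of stay.** "Length of hospitalization" is a secondary outcome, and the data collection form (Appendix A) has 6-hourly columns to 48 hours. Nothing says that every patient stays 36 hours.

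**The concern.** Opioid use to 36 hours and opioid use to discharge are different variables, and nothing in either document links them. The stated power belongs to the first, while the trial is to be judged on the second. Two separate consequences are possible.

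- **Precision.** If length of stay varies between patients but equally in both arms, the hospital-stay total picks up variance that has nothing to do with the block. Power falls, without bias.
- **Interpretation.** If the block changes time to discharge, the total mixes opioid need with hours observed, and a difference could partly reflect discharge timing. This is conditional. The protocol hopes that patients given both blocks may "achieve physical therapy milestones sooner than those who do not receive an genicular nerve block", but it states no expected difference in stay.

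There is also a reporting risk. With no window fixed in the SAP, either total could be reported as primary after the data are seen, and each could be defended from the protocol.

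**Working it through.** **1. Reproduce the protocol's figure (36-hour variable).** Inputs from Number of Local Participants: means 48 and 39 mg, SD 15, alpha 0.05, power 80%.

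- Effect size: d = (48 − 39)/15 = 0.60.
- Two-sided two-sample t-test (noncentral t): 44.59 per group.
- Wilcoxon-Mann-Whitney under normality, efficiency 3/π: 44.59 × π/3 = 46.69, rounded up to 47 per group, 94 in total.
- Power at 47 per group: 80.3% by this method, and 79.7% in 20,000 simulated normal trials.

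The protocol does not state sidedness. A one-sided test would need 37 per group, so the 94 is two-sided. It is correct for its own inputs.

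**2. What the hospital-stay total would need.** Its mean difference and SD. Neither document gives them, so no single corrected figure exists. Steps 3 to 5 are illustrations under stated assumptions.

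**3. Simplest case: the 9 mg difference is unchanged and only the SD grows** (47 per group, d = 9/SD, two-sided Wilcoxon).

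| Assumed SD (mg) | d | Power | Total N for 80% |
|---|---|---|---|
| 15 | 0.60 | 80% | 94 |
| 18 | 0.50 | 65% | 134 |
| 20 | 0.45 | 56% | 166 |
| 22.5 | 0.40 | 47% | 208 |
| 30 | 0.30 | 29% | 368 |

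If difference and SD grow in proportion, d stays at 0.60 and nothing is lost.

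**4. Effect scales with time, equal stays in both arms.** Simulation, 10,000 trials per setting. The 36-hour total is normal (48 or 39, SD 15, floored at 0). Hospital total = 36-hour total × F(stay)/F(36), where F(t) is cumulative use by hour t, with hourly use constant or falling 2% or 4% per hour. Stay is lognormal with mean 36 to 60 h, drawn independently of the patient's opioid use. CV is the coefficient of variation of stay.

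| CV of stay | Power, 47 per group |
|---|---|
| 0 | 80% |
| 10% | 76–80% |
| 20% | 68–79% |
| 30% | 58–78% |
| 40% | 48–76% |

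With no opioid effect the two-sided rejection rate is 4.8–5.4%, so this mechanism costs power only. Total N for 80% at a 48-h mean stay, for 0 / 2 / 4% hourly decline:

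- CV 20%: 124 / 106 / 100
- CV 30%: 158 / 120 / 104

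**5. Separate case: no opioid effect, active patients leave earlier** (48-h mean stay, CV 20–30%). With constant use the spurious saving can be checked by hand: 48/36 = 1.33 mg per hour, and 1.33 × 6 = 8.0 mg for discharge 6 h earlier.

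| Hourly decline | Spurious saving, 6 h earlier | Significant in favour of block (nominal 2.5%) | Planned effect on the same total |
|---|---|---|---|
| 0% | 8.0 mg | 29–38% | 12.0 mg (9 × 48/36) |
| 2% | 4.4–4.5 mg | 18–21% | 10.5–10.7 mg |
| 4% | 2.4–2.5 mg | 10% | 9.8–9.9 mg |

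Discharge 2 h earlier gives 0.8–2.7 mg and 4–7%. The two mechanisms oppose each other. With the planned effect and discharge 6 h earlier, significance is 94–98% at 0–2% decline and about 91–93% at 4%, partly because of discharge timing.

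**The case against.** The strongest reply is that no loss of power has been shown. Step 3 reaches down to 29% and step 4 only to 48%, because one holds the effect at 9 mg and the other lets it grow with time. Neither rests on data in the documents, and proportional scaling keeps both the 80% and the 94. Step 4 also assumes that stay is independent of opioid use and that the block's proportional effect lasts throughout; either assumption could move the result. All of this stands. The totals of 100 to 158 patients are not estimates.

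The discharge-timing case is open to a similar reply. No shorter stay is predicted, the surgeon and the follow-up staff are blinded, and length of stay is itself an outcome, so a difference would be visible. That makes the case secondary, though seeing a difference in stay would not separate it from the opioid result.

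There is also a real argument for the hospital-stay total: it can be checked against the chart, whereas a 36-hour total needs patient recall of doses after early discharge. That is a fair reason to prefer it, provided the sample size is then worked out for it.

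None of these points removes the mismatch. No text in either document equates the two windows.

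**Conclusion.** The concern holds. The 94 is not miscalculated, and power is not necessarily below 80%. The stated power simply does not belong to the stated primary outcome, and the documents contain nothing from which power for that outcome could be derived. Where stay varies little, the consequence is small: at most about 4 points of power at a CV of 10%. Where stay varies widely, it could be large. Those sizes rest wholly on assumed stays and hourly use. The inconsistency itself rests on the text alone, and because it concerns the primary outcome it should be settled before any analysis.

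**What to change.** **Change.** In both the protocol and the SAP, define the primary outcome as cumulative opioid consumption from end of surgery to 36 hours, in IV morphine equivalents. For a patient discharged before 36 hours, add opioids taken at home up to that hour, asked at the 48-hour call. The protocol already provides that "A study team member will follow up patients by telephone (if discharged prior to) at 48 hours, 72 hours and at 3 weeks". Report the hospital-stay total as a secondary outcome beside length of stay.

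**Alternative.** If the sponsor prefers the hospital-stay total as primary, restate sample size and power using a sourced mean and SD for that total.

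**Cost.** One sentence in each document and one added question, since the call's listed topics are pain, "narcotic side effects, and satisfaction with pain control", not doses taken. The form already has 6-hourly medication columns to 48 hours. No extra patients are needed.

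**Downside.** Home doses would be self-reported, because the chart check covers only the hospital stay and the pain journal (Appendix C) records scores, not doses. Under the simulation's assumptions:

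- 48-h mean stay (CV 20–30%): 9–20% of patients leave before 36 h, and at most 3% of the 36-hour dose is taken at home.
- 36-h mean stay (CV 20–40%): 54–58% of patients, and 4–15% of the dose.
- A 50% random reporting error on the home part leaves power at 76–81%.
- With no opioid effect, discharge 6 h earlier on a 48-h stay and home use under-reported by 30%, the spurious saving is 0.2–0.5 mg and the rate of significant results favouring the block is 2.8–3.3% (nominal 2.5%).

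Unanswered calls were not modelled, so the SAP should say how a missing home dose is handled.
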